**I. BACKGROUND AND SIGNIFICANCE**

*a. Historical Background*

***Childhood Survivors are a growing population in need of medical surveillance.***

Children diagnosed with cancer have experienced improved survival rates over time, with more than three-fourths becoming long-term survivors. However, survivors of childhood cancer often face new and continued health care challenges and require ongoing care to monitor and treat long-term effects of their cancer and treatment throughout adulthood. Ongoing medical treatment and surveillance, with access to quality healthcare and coverage, are critical.

***Although quality health insurance coverage is critical to this population, it has been complex to obtain.*** Given their ongoing health care needs, obtaining and navigating health insurance coverage is vital to ensure access to needed survivorship care. However, this can be difficult for individuals with pre-existing conditions such as a cancer diagnosis, who have historically faced denials of coverage, steep premiums, or “job lock” that keeps them from changing jobs for fear of losing coverage. At the same time, childhood survivors have had higher rates of uninsurance, unmet health care needs, and burdensome costs. These survivors are also less likely than siblings to be employed, married, and have a higher household income. [name] found that childhood survivors and siblings had similar rates of coverage, yet they differed by types of coverage and experiences obtaining coverage. Uninsured survivors in particular were more likely to experience financial burdens from medical care that affected their care utilization.

***Health care reform offers opportunities for childhood survivors to obtain quality coverage.*** The ACA was signed into law in 2010 and is intended to increase access to affordable, quality health care. ACA policies offer considerable opportunities for populations with pre-existing conditions like childhood survivors to obtain coverage and improve access to needed care. [name] and colleagues delineated the implications of specific ACA provisions for insurance coverage for childhood survivors.

**Although the ACA has increased coverage rates, uninsurance and underinsurance may remain a problem for childhood survivors.** The ACA and other unprecedented changes to the health care landscape offer both opportunities and risk to childhood survivors regarding insurance adequacy and underinsurance. From [name] 2011-2012 CCSS (Childhood Cancer Survivor Study) health insurance survey we found that childhood survivors lacked awareness about the ACA and had concerns that the ACA would increase their costs and threaten their quality and continuity of coverage. While the ACA requires coverage with no out-of-pocket costs for preventive services with "A" or "B" U.S. Preventive Services Task Force (USPSTF) ratings, these guidelines are not based on survivor-specific preventive guidelines and, as such, may not cover personalized screening recommendations.

**Limitations in health insurance literacy can make choosing and using health insurance challenging.** With the complex and confusing array of evolving insurance designs, being able to understand and navigate insurance benefits is crucial for survivors to obtain the health care they need. However, many people have inadequate understanding of available insurance benefits and resources, and have limited health insurance literacy (i.e. perceived knowledge, ability, and confidence to make informed decisions about choosing and using health insurance). Vulnerable populations, such as those with low income and poorer health, are more likely to have limited health insurance literacy. Understanding specific insurance benefits and larger ACA policies may help survivors maximize coverage and prevent unmet need and burdensome costs.

**Patient navigation interventions help patients overcome health care barriers.** Patient navigation is a patient advocacy approach that was introduced in 1990, by [name], to decrease high rates of breast cancer death among Black women in Harlem. Patient navigation aims to reduce cancer disparities and negative health outcomes among vulnerable patient populations. Patient navigators were envisioned as proactive patient advocates who provided logistic and emotional support to promote patients' access to timely care.

**Existing navigator programs offer limited assistance with understanding and managing health insurance benefits and costs.** The US healthcare system is complex. Even with reform under the ACA, understanding insurance options remains complicated and a source of frustration for consumers. While addressing insurance barriers to accessing care may be a component of some navigator programs, navigators focused specifically on helping patients understand and use their insurance benefits are rare. Navigator services mandated by the ACA in health insurance exchanges are available to help consumers choose and enroll in coverage, but their reach does not extend beyond enrollment. Many exchange enrollees have sought navigation services post-enrollment to help understand their new insurance plans, but such post-enrollment services are unavailable. At the same time, cost-sharing under the ACA will continue to increase as coverage was not stabilized by Congress via payments to insurers to

reduce costs for consumers. Survivors in particular are going to need comprehensive assistance with insurance in future years.

***b. Previous Studies***

***Childhood survivors and health insurance.*** In 2005 [name] published findings in the *Journal of Clinical Oncology* demonstrating that CCSS survivors, compared to siblings, were significantly more likely to be uninsured and have difficulties obtaining health insurance. In 2009-2010 she conducted in-depth interviews with a subset of CCSS survivors and with Drs. [name], [name], and [name] found that survivors had low coverage expectations, had difficulties understanding how to utilize their coverage, and inevitably worried about future health care costs. This team surveyed a randomly selected sample of CCSS participants and siblings about their health insurance coverage and perspectives about the ACA. Survivors were significantly less likely to have employer-sponsored coverage (79.4% vs. 86.0%; p=0.04) and more likely to be covered by Medicaid/State (12.3% vs. 4.4%; p=0.002). 15.4% of survivors vs. 1.6% of siblings had recently been denied insurance (p<0.001). Survivors were more likely to borrow money to pay medical expenses (17.3% vs. 9.0% siblings; p=0.002) and not fill a prescription due to cost (15.7% vs. 9.0% siblings; p=0.02). Only 27.3% of survivors and 26.2% of siblings reported familiarity with the ACA. Concerns about the ACA included costs, decreased access to quality coverage, and employment. The majority of survivors, across different types of insurances, indicated strong interest in an insurance education program.

***Recent study team reports of childhood survivors' underinsurance and its effects on financial burden and health care utilization.*** [name] led analyses describing patterns of health insurance coverage and care accessibility and affordability in an NHIS sample of adult childhood cancer survivors compared to adults without cancer during 2010-2014. Significantly more childhood survivors reported being uninsured, delaying medical care (24.7% vs 13.0%), needing but not getting medical care (20.0% vs 10.0%), and having trouble paying medical bills (40.3% vs 19.7%), compared to controls (ps<0.0001). In 2017, [name] and the study team published findings in *JAMA Internal Medicine* and *JCO* documenting that, compared to siblings, childhood survivors were significantly more likely to endorse indications of being underinsured, including being 84% more likely to borrow money because of medical expenses, 80% more likely to worry about being unable to pay for a needed treatment, and 74% more likely to worry they wouldn't be able to afford to fill a prescription. In addition, childhood survivors were more likely to report spending a higher percentage of their income on out-of-pocket medical costs. Survivors reported spending almost more than \$1000 annual out-of-pocket costs compared to siblings. A higher percentage of income spent on out-of-pocket medical costs was significantly associated with survivors' problems paying medical bills (OR, 8.9; 95% CI, 4.4 to 18.0); deferring care for a medical problem (OR, 3.0; 95% CI, 1.6 to 5.9); skipping a test, treatment, or follow-up (OR, 2.1; 95% CI, 1.1 to 4.0); and thoughts of filing for bankruptcy (OR, 6.6; 95% CI, 3.0 to 14.3).

***Intervention and program development with childhood cancer survivors.*** [name] has studied the health behaviors and perceptions of childhood cancer survivors.

She directed an NCI-funded trial to decrease smoking rates among 796 CCSS smokers that was found to be efficacious. She published a qualitative paper that had shaped the intervention, as well as a process evaluation paper which examined intervention characteristics associated with cessation success. [name] also has extensive experience conducting qualitative research to inform survivorship program development. [name] is leading the development and testing of a childhood cancer survivor transition program with a focus on the provision of survivorship care plans for patients and families.

**Health insurance and individuals with chronic conditions.** [name] has extensive experience studying health insurance issues for individuals with chronic conditions, including Medicaid populations and groups with high expenditures. She has also studied unmet need, a commonly used measure of underinsurance. She conducted work on the private health insurance and work-life benefit systems for children with chronic conditions which resulted in guides for employers, families, and state employees. [name] work has demonstrated that children and families with chronic conditions are vulnerable to health insurance designs with high levels of cost-sharing and may reduce use of needed care due to cost. [name] published on coverage gaps, financial burden, and medical costs, and their impact on access to care among childhood, adolescent and young adult cancer patients and survivors.

**Effects of new insurance designs and health reform policies.** [name] led one of the first studies of health insurance exchange plans, which documented problems for exchange enrollees with financial burden and unexpected costs; this study also identified challenges with understanding and choosing plans for families, many of whom wished for greater assistance navigating plan options. [name] has conducted studies of unmet health care need and financial burden among children and families with chronic conditions in high-deductible and other insurance plans. She has examined the impact of increased cost-sharing on health care decision making and use of recommended health care services. She is conducting a trial to evaluate how a price transparency tool can help high-deductible plan enrollees manage costs.

**Peer counselor and navigator-based interventions.** [name] directed a smoking cessation trial, in collaboration with the Long-Term Follow-Up (LTFU) study at St. Jude Children's Research Hospital, in which she trained childhood cancer survivors to be smoking cessation peer counselors and deliver a phone-based intervention. [name] conducted a randomized trial of a patient navigator intervention to reduce readmissions for high-risk patients discharged from a safety-net hospital. [name] has conducted extensive survey research examining patient barriers to cancer screening and follow-up and physician referral communication with patients. She examined the effectiveness of a patient navigation program in improving minority patients' follow-up of an abnormal mammogram.

### **c. Rationale of Proposed Research**

Health care reform under the Patient Protection and Affordable Care Act (ACA) offers considerable opportunities for childhood cancer survivors to obtain coverage and improve access to needed care. However, in the general population, many people have low understanding of available insurance benefits and resources, and have limited health insurance literacy (i.e. perceived knowledge, ability, and confidence to make informed decisions about choosing and using health insurance). Misperceptions about which services require out-of-pocket costs may lead some enrollees to avoid services that are in fact exempt from cost sharing. Even with coverage protections from the ACA, barriers to obtaining quality coverage (e.g., in states without Medicaid expansion) and accessing needed care may remain for childhood survivors. Understanding and navigating insurance benefits is crucial for cancer survivors to obtain the health care they need. In this new post-reform landscape, the degree to which coverage and costs have changed for childhood cancer survivors is still largely unknown.

#### ***d. Study Site Roles***

The sites in this study, MGH, St. Jude Children's Research Hospital, and the University of Utah will each have different, complementary roles. The Partners IRB will be the IRB of record for this study, and the collaborating IRBs of St. Jude and the University of Utah will CEDE review to the Partners IRB. Site and IRB roles are described below.

#### **MGH Site Roles**

As the IRB of record and lead site for this study, MGH will be responsible for the development and regulation of all study-related materials, documents, assessments, and interventions. For Phase 1 of the study, MGH will be specifically responsible for the facilitation of advisory board and participant focus group interviews, and the qualitative analysis this data. Utilizing the data garnered from these interviews, MGH will further develop and tailor the intervention content (though MGH will work with collaborators on this aspect of the study, MGH will lead in the development and final submission of this piece).

For Phase 2 of the study, MGH will be responsible for the delivery of the intervention content. Through the platform of MGH telehealth (Zoom), approximately 40 intervention arm participants (recruitment processes are described below) will receive brief health insurance educational sessions by a health insurance navigator. MGH will be responsible for the training and supervision of the navigator.

For Phase 3 of the study, MGH will be responsible for the facilitation and analysis of exit interviews conducted with the Phase 2 intervention arm participants (MGH will not be conducting the exit interviews. See University of Utah Phase 3 roles for more information).

#### **St. Jude Site Roles**

As one of the collaborating sites for this study, St. Jude will be responsible for all recruitment activities. St. Jude Children's Research Hospital is the site of the Long-Term Follow-up Study (LTFU), and study participants will be exclusively recruited from the

eligible members of this cohort. St. Jude will be responsible for recruiting, randomly selecting, and consenting participants for the focus group interviews, the open pilot of the study intervention, and the pilot randomized trial. Once recruited and consented, St. Jude will securely send relevant participant information to the study staff at the University of Utah and MGH.

## **II. SPECIFIC AIMS**

### **Aim 1: To develop a psychoeducational health insurance navigation program (HINP).**

A1a: To qualitatively assess LTFU participants' reports of 1) barriers to accessing and using quality health insurance2) resources to support health insurance access and use, 3) navigation program content, 4) intervention structure and dose, 5) program delivery, 6) program acceptability, 7) aspects of coverage that are not well understood

A1b: Aim 1b: To qualitatively assess approximately 3 advisory boards' and approximately 10 individual experts' feedback 1) barriers, 2) resources, 3) content, 4) intervention structure and dose, 5) delivery and 6) selection criteria A1c: To pilot the intervention with LTFU participants (approximate n=10).

### **Aim 2: To conduct a videoconferencing-based pilot randomized trial of the HINP (n= approximately 80).**

A2a: To assess the feasibility (number of eligibles enrolled and sessions completed) and acceptability (satisfaction, perceived support) of participants undergoing the HINP.

A2b: At 3-month post-program follow-up, to assess the efficacy of the HINP to assist participants with accessing and utilizing coverage and managing costs. Primary

outcomes are 1) health insurance literacy and 2) financial distress related to medical costs

**A2b Hypothesis:** The HINP, compared to enhanced usual care, will improve participants' health insurance literacy and decrease financial distress.

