### Intervention Assignment and Randomization

#### Pilot Trial

The CCSS Coordinating Center LTFU study staff will randomly select 80 participants among the LTFU cohort (original and expanded together). To do this, CCSS will use stratified random sampling, where we will divide the sample of LTFU participants into two groups: residing in a Medicaid expansion state or not. Random samples will then be selected from each of the two strata until 80 participants are consented and enrolled. The 80 selected participants will be randomized to either enhanced usual care (n=40), or the health insurance navigation intervention (n=40). After obtaining informed consent, participant information will be sent securely to [name] via SharePoint, an encrypted system used to transfer data. [name] team will lead the pilot trial procedures.

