#### **Quantitative Data**

For quantitative data, [name] team at HCI will conduct the analyses with input from [name] and her study team, and the LTFU study team. As discussed in Participants, we will sample by Medicaid expansion vs. non-expansion states. All analyses will be weighted using inverse sampling probabilities so that results are representative of the overall LTFU study cohort.

At baseline, all pilot participants will complete a baseline. The HINP navigator will use each participant's baseline survey responses to personalize and individualize sessions. At the 3-month post-program follow-up, participants will complete the Phase 1 survey Outcome questions, which will be asked within the 5-month time frame period after trial enrollment. Participants will also be asked questions below about feasibility and acceptability.

We will use descriptive statistics to report on the following endpoints: intervention feasibility (percent of participants enrolled), acceptability (satisfaction, perceived support) and efficacy (e.g., ACA familiarity, health insurance literacy, intention to adhere to recommended survivorship care, provider communication, and coverage status).

Descriptive statistics will examine group differences at baseline; any imbalances will be adjusted. We will use chi square and independent t-tests to compare end-of-intervention changes in preliminary efficacy outcomes between the two groups. Although a 3-month post intervention follow-up period is brief, we will also conduct exploratory comparisons with other study outcomes to see if trends change in the expected direction. We will compare pre/end-of-treatment, within groups, with paired t-tests. In addition, we will use bivariate statistics to examine sociodemographic and cancer-related factors (type of

diagnosis, age at diagnosis, years since diagnosis, cancer treatment, chronic conditions, cancer treatment (e.g., cranial radiation yes/no, anthracycline exposure yes/no) associated with feasibility, acceptability and preliminary efficacy outcomes.

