## Measures

To evaluate the pilot, we will use a mixed methods data collection approach, using both quantitative survey items and open-ended questions. Most study measures will come from survey questions repeated from the 2011-2012 CCSS health insurance survey (see Appendix); some new questions will be added and are indicated as such. Survey development included a qualitative study conducted with a sample of LTFU participants, modifications and inclusions of national survey questions and a cognitive testing phase. Using data collected previously by the overall LTFU via abstraction of medical records, data will be used to provide information on cancer diagnosis, age at diagnosis, and cancer treatment. These data will be provided to [name] team via SharePoint, an encrypted system used to transfer data. Data from the LTFU surveys will provide information on sociodemographic and medical history since cancer treatment, and presence of a medical late effects and chronic health conditions including second cancers. The measures will include the following:

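### For yes/no efficacy items, chi-square on change can waste up to about half the available power; the follow-up answer should be compared within baseline answer

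*Combined protocol and SAP*

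**What the plan says.** The A2b hypothesis in Specific Aims is that HINP, against enhanced usual care, will improve "health insurance literacy and decrease financial distress".

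The between-arm analysis is in Biostatistical Analysis, Quantitative Data: "We will use chi square and independent t-tests to compare end-of-intervention changes in preliminary efficacy outcomes between the two groups". Chi-square can only be meant for the categorical items. The section does not define change for such an item. Its one provision for baseline is: "Descriptive statistics will examine group differences at baseline; any imbalances will be adjusted". No model is named.

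The Measures section says: "Most study measures will come from survey questions repeated from the 2011-2012 CCSS health insurance survey". Previous Studies reports financial items from the team's own survey as percentages. On borrowing it says: "Survivors were more likely to borrow money to pay medical expenses (17.3% vs. 9.0% siblings; p=0.002"). A second item from that survey is whether people did "not fill a prescription due to cost (15.7% vs. 9.0% siblings; p=0.02"). A national survey sample described in the same section gives "having trouble paying medical bills (40.3% vs 19.7"%). Under Secondary Outcomes, the two questions on discussion with providers are explicitly yes/no.

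The Pilot Trial section fixes the arms: "randomized to either enhanced usual care (n=40), or the health insurance navigation intervention (n=40").

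**The concern.** For a yes/no item asked twice there are four possible histories: yes/yes, yes/no, no/yes and no/no. Coding change as improved, same or worse puts yes/yes and no/no in one cell, although one is a failure and the other the best possible result. A program that resolves existing problems and prevents new ones shrinks the first group and enlarges the second, so part of its effect cancels inside the cell. The two cells that remain informative are small when the problem is uncommon.

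The follow-up answer, read within groups defined by the baseline answer, keeps all four histories apart and needs no extra data. At 40 per arm, the choice affects how much the pilot can show about one of the two outcomes named in A2b. The t-test on continuous scores is a separate matter and is not questioned here.

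**Working it through.** The plan states no power, effect size or significance level, so there is no figure of its own to reproduce.

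**Inputs from the documents.** n = 40 per arm. Background rates p = 17.3% (borrowed money), 15.7% (prescription not filled) and 40.3% (trouble paying bills).

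**Assumptions, none stated in the documents.** Yes/no format; change coded improved/same/worse; two-sided 5%; full follow-up; unweighted; control rate stable over time; persistence a (the chance that a control participant with the problem still has it at follow-up) of 60-80%.

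**Who can improve.** n × p:
- 40 × 0.173 = 6.9
- 40 × 0.157 = 6.3
- 40 × 0.403 = 16.1

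**Cell sizes at 17.3%.** A stable rate requires a new-problem probability b = p(1 − a)/(1 − p).
- a = 0.6: b = 0.173 × 0.4/0.827 = 0.084. Expected improved = 40 × 0.173 × 0.4 = 2.8, and the same number worsened.
- a = 0.8: b = 0.173 × 0.2/0.827 = 0.042. Expected improved = 40 × 0.173 × 0.2 = 1.4, and the same number worsened.

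With no effect, four of the six cells of the 2×3 table therefore expect only 1.4-2.8 people.

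**How the effect cancels (17.3%, a = 0.6, HINP halves both a and b).**

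| | Control | HINP |
|---|---|---|
| yes/yes | 40 × 0.173 × 0.6 = 4.2 | 40 × 0.173 × 0.3 = 2.1 |
| no/no | 40 × 0.827 × 0.916 = 30.3 | 40 × 0.827 × 0.958 = 31.7 |
| same (sum) | 34.5 | 33.8 |
| yes at follow-up | 6.9 | 3.5 |

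The follow-up rate has halved, yet the same cell has hardly moved.

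**Power by simulation, 40 per arm.** Ranges run over a = 60-80%. Repeat runs agree to within a point or two.

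| Scenario | Chi-square on 3-category change | Mantel-Haenszel on follow-up, stratified by baseline |
|---|---|---|
| 17.3%, no effect | 2-4% | 4-5% |
| 17.3%, halved in everyone | 11-16% | 24-31% |
| 40.3%, halved in everyone | 26-43% | 54-64% |
| 17.3%, only persistence halved | 9-14% | 10-19% |
| 17.3%, only persistence removed | 22-45% | 30-60% |
| 40.3%, only persistence halved | 21-42% | 21-43% |

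Here, in everyone means that a and b are both cut by the same fraction. The only-persistence rows leave b unchanged, so HINP helps only people who had the problem at baseline.

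**Relative loss, 1 − (change power/stratified power).**
- 17.3%, halved in everyone: 1 − 11/24 = 54% and 1 − 16/31 = 48%.
- 40.3%, halved in everyone: 1 − 26/54 = 52% and 1 − 43/64 = 33%.
- 17.3%, only persistence halved: 1 − 9/10 = 10% and 1 − 14/19 = 26%.
- 40.3%, only persistence halved: about nil.

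**Other readings of changes.**
- Follow-up status alone, 17.3% halved in everyone: 22% against 24-31% stratified, a loss of 8-29% (1 − 22/24 and 1 − 22/31).
- Improved/not coding at a 16.5% rate, baseline/follow-up correlation 0.4, 0.6 and 0.8. Halved in everyone: 10.2%, 15.7% and 25.5%, against 20.8%, 24.4% and 31.5% with baseline adjustment. Only persistence halved: 10.1%, 15.7% and 25.4%, against 8.2%, 12.4% and 21.6%, so this coding does slightly better there.

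**The case against.** **The format and the coding are inferred.** Outcome Measures lists financial topics without response formats, and the survey instruments are not in the text available. If financial distress is scored as a scale, the t-test applies and this argument does not. Nor does the plan prescribe an improved/same/worse table; chi-square on follow-up status is a natural reading. This stands, and the point is limited accordingly to items that are yes/no.

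**The loss depends on how HINP works.** A reader might infer that the planned test necessarily loses half or more of the power. The documents do not support that. The figure needs HINP to prevent new problems as well as resolve existing ones. If it acts only on those affected at baseline, the loss is modest at 17.3% and absent at 40.3% with persistence halved.

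**The rates are background figures.** A reader might also take 6-7 of 40 as a ceiling for financial distress generally. It is an expected count for two items. Previous Studies gives 20.0%, 24.7% and 40.3% for related items, and none of these rates is a design assumption of the trial.

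**It is a pilot.** Pilot Trial Design sets about 40 per arm for feasibility, acceptability and exploration. The Outcomes section makes efficacy secondary, although A2b calls these two outcomes primary. Halving a 17.3% rate is hard to detect by any method. Inferring that the sample size is wrong would therefore be a mistake. What remains is a question of efficiency and interpretability, which still matters when the stated purpose is to explore differences.

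**Conclusion.** The point holds in conditional form. For yes/no items the plan's wording permits a change analysis that pools opposite results, and it prespecifies no use of the baseline answer beyond adjusting for imbalances that happen to appear. With improved/same/worse coding, 60-80% persistence and an effect in everyone, the cost is about half the power at 17.3% and about a third to a half at 40.3%. It is smaller under a follow-up-status reading, and small or nil if only people already affected benefit. In none of these three-category or follow-up-status scenarios does stratifying by baseline do materially worse. Only improved/not coding, with benefit confined to those already affected, comes out slightly ahead. The pooling of persistent with never-present problems follows from the coding alone. The power figures rest on the listed assumptions.

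**What to change.** In Quantitative Data:

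- For yes/no efficacy items with a baseline answer, compare the follow-up answer between arms, stratified by (or adjusted for) the participant's own baseline answer. Report a Mantel-Haenszel risk difference with 95% interval, applying the plan's inverse-probability sampling weights where those are used.
- Report counts improved and worsened by arm descriptively.
- For items with no baseline answer, compare follow-up status alone.
- Do not add an automatic switch to an exact test when expected counts fall below 5. At 17.3% a stratified exact test rejects only 2.0-2.9% of the time with no effect, and its power for a halved rate is 18-22%. If an exact-type test is wanted, use a mid-p version.
- State which items are yes/no and how financial distress is scored.

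The cost is a few sentences of analysis text. No new data, participants or visits are needed.
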